## Clinical Investigation Plan

Primary Safety Event	Description
	
intracranial angioplasty); OR available neuroimaging documents a new hemorrhage or infarct; OR the neurological deficit results in death.
 
 
• No other readily identifiable non-stroke cause for the clinical presentation (e.g. brain tumor, trauma, infection, hypoglycemia, peripheral lesion, pharmacological influences).
 
• Confirmation of the diagnosis by at least one of the following: neurology or neurosurgical specialist; neuroimaging procedure (MRI or CT scan or cerebral angiography); lumbar puncture (i.e. spinal fluid analysis diagnostic of intracranial hemorrhage)
 

Thromboembolism	An arterial or venous thrombus that results in deep vein thrombosis, pulmonary embolism, or peripheral arterial embolism.
Transient ischemic attack	New focal neurological deficit of vascular (occlusive) origin with rapid symptom resolution (usually 1 to 2 hours), always within 24 hours determined by the consulting neurologist; neuroimaging without tissue injury.
Vagal nerve injury/gastroparesis	Vagal nerve injury is defined as injury to the vagal nerve that results in esophageal dysmotility or gastroparesis. Vagal nerve injury is considered to be a major complication if it prolongs hospitalization, requires hospitalization, or results in ongoing symptoms for more than 30 days following an ablation procedure
Vascular access complication	Vascular access complications include development of a hematoma, an AV fistula, or a pseudoaneurysm. A major vascular complication is defined as one that requires intervention, such as surgical repair or transition, prolongs the hospital stay, or requires hospital admission.

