### 4.0 ENDPOINTS

#### 4.1 Primary Endpoints and Rationale

##### 4.1.1 Primary Safety Endpoint

The primary safety endpoint is the rate of device and/or procedure-related serious adverse events with onset within 7-days of any ablation procedure that uses the TactiFlex SE catheter (initial or repeat procedure performed 31-80 days of initial procedure) that are defined below:

- Atrio-esophageal fistula
- Cardiac tamponade/perforation
- Death
- Heart block
- Myocardial infarction
- Pericarditis
- Phrenic nerve injury resulting in diaphragmatic paralysis
- Pulmonary edema
- Pulmonary vein stenosis
- Stroke/cerebrovascular accident
- Thromboembolism
- Transient ischemic attack
- Vagal nerve injury/gastroparesis
- Vascular access complications (including major bleeding events)

. Atrio-esophageal fistula, cardiac tamponade/perforation and pulmonary vein stenosis will be evaluated through 12-months.

. Bleeding is a major complication of AF ablation if it requires and/or is treated with transfusion or results in a 20% or greater fall in hematocrit.

These events must meet the criteria listed in **Appendix II** to be included in the primary endpoint as adjudicated by the Clinical Events Committee (CEC).

The performance goal for the Primary Safety Endpoint for this clinical trial

= 12.9%.

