### 6.4 Pre-Discharge Visit (In-hospital)

Patients may be discharged at the discretion of the investigator after the required testing, listed below, has been performed, which includes a neurologic assessment 12-36 hours after the procedure. This may require the subject to stay in the hospital the night after the procedure. It is strongly recommended that the investigator performing the ablation procedure personally evaluates the subject the evening after the procedure and/or the morning following the procedure and maintains active surveillance of the subject's postoperative care and condition for at least 72-hours or prior to discharge, whichever occurs first.

The following are required testing for the Pre-Discharge Visit:

- Complete physical exam
- 12-lead ECG
- Neurological assessment by a qualified physician and administration of the NIHSS by a certified assessor must be performed  $\geq 12$  hours post-procedure prior to discharge, but no later than 36 hours after the procedure.

NOTE: Subjects with new findings on the neurologic assessment/NIHSS are required to have a formal neurological consult and follow-up diffusion-weighted magnetic resonance imaging (MRI) of the brain. If contra-indicated for MRI, then an alternate form of imaging may be performed.

- Document AAD and anticoagulant drug usage
- Document adverse events and protocol deviations
  - If the subject describes symptoms suggestive of cardiac tamponade (i.e., chest pain with hypotension) or if cardiac tamponade is suspected, the subject should be evaluated promptly by the investigator and a TTE performed.

If the subject requires an extended hospitalization due to a complication or other reason, the neurological exam and NIHSS assessment should be performed within 36-hours of the procedure. All other pre-discharge testing should be performed prior to discharge, but no later than 72 hours post-procedure.

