##### 7-Day (7 ± 2 days) Follow-up Visit

This visit constitutes a phone call to the subject (but may also be performed in-person) after each ablation procedure (initial and if applicable, a repeat procedure) and requires documentation of the following:

- Document AAD and anticoagulant drug usage
- Document adverse events and protocol deviations
  - If the subject describes symptoms suggestive of pulmonary vein stenosis (e.g. shortness of breath, cough, and hemoptysis), have the subject schedule a visit with the investigator to determine if CT or MRI imaging of the pulmonary veins should be performed.
  - If the subject describes symptoms suggestive of atrio-esophageal fistula such as chest pain, painful swallowing, fever, and/or describes symptoms of stroke, have the subject schedule a visit with the investigator immediately or go to the emergency room based on the severity of the symptoms.
  - If the subject describes symptoms suggestive of cardiac tamponade (i.e., chest pain with hypotension) or if cardiac tamponade is suspected, the subject should be evaluated promptly by the investigator and a TTE performed.

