### 10.9.4 Clinical Events Committee (CEC)

The Clinical Events Committee (CEC) is an independent adjudication body comprised of qualified physicians who are not participants in the clinical investigation. The CEC will review and adjudicate all AEs that are determined by the Sponsor's Safety personnel to potentially meet the criteria of 1) a serious AE and/or 2) an AE related to the investigational devices or ablation procedure. The AE definitions provided in this CIP will be used and the CEC will be governed by a CEC charter. The CEC's adjudication of the reported adverse event data will be used for analysis.

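### A serious transient neurological deficit that resolves without brain imaging can meet neither the TIA nor the stroke definition, and so drops out of the primary safety endpoint

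*Protocol*

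**What the plan says.** **What counts.** Protocol Section 4.1.1 lists TIA among 14 components of the primary safety endpoint. An event must be serious, related to the device or procedure, and begin within 7 days of an ablation with the study catheter (three other components are followed for longer). It must also satisfy Appendix II, as judged by the Clinical Events Committee (CEC). Section 10.9.4 adds: "The AE definitions provided in this CIP will be used and the CEC will be governed by a CEC charter".

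**The TIA row of Appendix II.** It describes a new focal deficit of vascular origin whose symptoms clear quickly, usually in 1 to 2 hours, and "always within 24 hours determined by the consulting neurologist; neuroimaging without tissue injury".

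**The stroke row of Appendix II.** A deficit lasting less than 24 hours qualifies only if a therapeutic intervention was given, if imaging shows a lesion ("OR available neuroimaging documents a new hemorrhage or infarct"), or if the deficit causes death. The diagnosis may be confirmed by any one of several routes.

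**When imaging is mandated.** Section 6.4 says: "Subjects with new findings on the neurologic assessment/NIHSS are required to have a formal neurological consult". Diffusion-weighted MRI follows, or another form of imaging if MRI is contraindicated. Section 6.1 and Table 4 note 9 use the same trigger. Table 4 marks brain MRI only in the baseline and pre-discharge columns. The scheduled post-procedure examination takes place at 12 to 36 hours.

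**After discharge.** For stroke symptoms reported at the 7-day contact, Section 6.6.3 tells the site to "have the subject schedule a visit with the investigator immediately or go to the emergency room based on the severity of the symptoms". It names no brain imaging.

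**The concern.** As worded, the TIA row makes a negative scan part of the definition, but the protocol does not ensure that a scan exists for every transient deficit. The row itself says that symptoms usually clear in 1 to 2 hours, whereas the scheduled examination comes at 12 hours or later. The stroke row refers only to imaging that is available; the TIA row has no such qualifier.

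At stake is the count in a single-arm comparison with a fixed goal of 12.9%. If a missing scan is read as a failed criterion, missing information becomes no event, and the trial's own safety rate can only go down. Two adjudicators could also classify the same record differently, depending on how strictly they read the row.

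**Working it through.** The plan gives no figure to reproduce on this point. The safety sample-size calculation, alpha, expected rate and test are redacted. The check is therefore a trace through the definitions, followed by an indication of scale.

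**Step 1. One record, three imaging states.** Take a hypothetical subject with hemiparesis on day 4 at home that resolves in two hours. The subject is admitted (hence serious under Section 7.1.2), the event is judged procedure-related, a neurologist considers it a TIA, and no intervention is given.

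| Brain imaging | TIA row | Stroke row | Counted? |
|---|---|---|---|
| Done, no lesion | met | not met | yes, as TIA |
| Done, new lesion | not met | met through the imaging route | yes, as stroke |
| Not done | not met as written | not met: under 24 hours, no intervention, no lesion shown, no death | no |

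The first two rows cover both possible scan results, and each leads to a counted event. Only the absence of the scan removes it. No visible text supplies a fallback category.

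**Step 2. Can the protocol's own pathway leave the event unimaged?** Yes, in two ways.

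- In hospital: a deficit at hour 3 that has gone by hour 5 can leave a normal examination at hour 18, and then nothing triggers imaging.
- After discharge: the 7-day contact leads to a visit or the emergency room, where imaging is possible but not required.

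**Step 3. Scale.** Inputs from the documents are the goal of 12.9% (Section 4.1.1), 305 main-study subjects (Section 5.6), and a tested parameter that is the percentage of subjects with an event (SAP 2.3.1.1). Assumed inputs are an exact one-sample binomial test, one-sided alpha of 0.025 or 0.05, and all 305 subjects evaluable.

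- One uncounted subject: 1/305 = 0.33 points. Two: 2/305 = 0.66. Three: 3/305 = 0.98.
- The pass limit is the largest c with P(X ≤ c | 305, 0.129) ≤ alpha.
  - Alpha 0.025: c = 27 (27/305 = 8.9%), P = 0.018. The exact upper limit is 12.6% at 27 events and 13.0% at 28.
  - Alpha 0.05: c = 29 (29/305 = 9.5%), P = 0.042. The exact upper limit is 12.7% at 29 events and 13.1% at 30.
- With 290 evaluable the limits are 26 and 27; with 275 they are 24 and 26.

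Suppose uncounted events lower the observed rate by an assumed 0.2, 0.5 or 1.0 points, and the true rate is exactly 12.9%. The chance of passing then rises from 1.8% to 2.3%, 3.2% or 5.6% (limit 27), and from 4.2% to 5.2%, 7.0% or about 11% (limit 29). These are worst-case illustrations: the documents give no TIA rate, and the calculation supposes that the affected subjects have no other primary safety event.

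Far from the goal the effect almost vanishes. At a true rate of 6%, the trial already passes with probability 98.2% (limit 27) or 99.4% (limit 29), so an undercount can add at most 1.8 or 0.6 points.

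**The case against.** **The pathway is better than it looks.** Section 6.4 requires a physician's neurological assessment as well as the NIHSS. A physician who knows that the patient was aphasic that afternoon could record this as a new finding even after recovery, which would make the consult and imaging mandatory. After discharge, stroke symptoms go to the investigator or the emergency room, where a scan is likely. This stands, and it limits the frequency. It does not close the gap, because neither route requires imaging once the deficit has cleared and the examination is normal.

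**Many unimaged TIAs would not count anyway.** The event must be serious and related. A brief, untreated deficit may fail on seriousness, and one that leads to admission is the most likely to be scanned. This also stands. The point is confined to events that meet those requirements and fail only for want of imaging.

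**Other rows need objective tests too.** Pulmonary vein stenosis needs CT or MRI, and phrenic paralysis a sniff test. There, however, a negative test means that the event did not occur. For a vascular focal deficit, both scan results lead to a counted event.

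**The row can be read loosely,** with negative imaging serving only to separate TIA from stroke. That is possible, and it is what the fix would make explicit. The contrast with the stroke row's qualifier favours the strict reading.

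**Two stronger conclusions are tempting and not supported.** A reader might infer that the trial is biased towards meeting its goal. The derivation of the goal is redacted. Protocol Appendix II says most definitions were adapted from a consensus statement, and SAP 1.4.1.1 says the goal came from relevant studies. If those studies ascertained TIA in the same way, the goal already reflects it. SAP Appendix A is not readable and the CEC charter is not supplied, so a remedy could also sit there. A reader might likewise infer that the neurologist's determination should be replaced by the CEC's. That would be a debatable departure from the adapted definitions, and it is not needed for this point.

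**Conclusion.** The gap in the wording is real. Under Appendix II as written, a serious, related, vascular focal deficit that resolves within 24 hours without imaging or intervention can meet neither row, although either scan result would have made it a primary safety event (for TIA, given the neurologist's determination as well).

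The consequence is a possible undercount, not a systematic loss of TIAs: those imaged in routine care are still counted. Its frequency cannot be taken from the documents and is probably small. Each event is worth 0.33 points and changes the conclusion only near 27 to 29 events, under the assumed test, alpha and denominator. The undercount concerns the trial's own rate; distortion relative to the 12.9% goal is not shown. The change is worth making because it is cheap and removes an ambiguity from a primary endpoint definition.

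**What to change.** In the Appendix II TIA row, change the imaging element to: *neuroimaging, where obtained, without tissue injury*. Add that an event otherwise meeting the definition, including the seriousness and relatedness requirements of Section 4.1.1, counts as a TIA when no neuroimaging was obtained. Make the same change in SAP Appendix A and the CEC charter if they repeat the row.

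In the report, state how many TIAs were counted without imaging, and give the primary safety rate with and without them.

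The cost is wording in up to three documents and one extra line of reporting, with no added visit or test. The downside is that an occasional TIA mimic may be counted, which makes the safety rate slightly less favourable; the second rate shows by how much.

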## Clinical Investigation Plan

### APPENDIX III: SITE CONTACT INFORMATION

Contact information for each participating clinical site is available under separate cover by contacting the Sponsor.

### APPENDIX IV: LABELS

Copies of all current labeling and Instructions for Use documents for investigational devices listed in Section 2.2.3 will be provided under separate cover.

### APPENDIX V: CASE REPORT FORMS

Final draft case report forms (CRFs) will be provided to FDA under Separate Cover as part of the IDE Submission.

### APPENDIX VI: INFORMED CONSENT FORM

A template informed consent form will be provided under separate cover.

### APPENDIX VII: MONITORING PLAN

A copy of the Monitoring Plan can be obtained upon request from the Sponsor Clinical Project Manager for the clinical investigation.

### APPENDIX VIII: SPONSOR'S CLINICAL SAFETY GROUP CONTACT INFORMATION

### APPENDIX IX: REVISION HISTORY

This CIP may be amended as appropriate by the Sponsor. Rationale will be included with each amended version in the revision history table below. The version number and date of amendments will be documented.

IRB/EC and relevant Regulatory Authorities, if applicable, will be notified of amendments to the CIP.

Amendment Number	Version	Date	Details	Rationale
Not Applicable	A	29-May-2020	Initial release of CIP	N/A

## Clinical Investigation Plan

### APPENDIX X: CIP SUMMARY

Clinical Investigation Name	TactiFlex PAF IDE [REDACTED]
Title	Safety and Effectiveness of TactiFlex™ Ablation Catheter, Sensor Enabled™ (TactiFlex SE) for the Treatment of Drug Refractory, Symptomatic, Paroxysmal Atrial Fibrillation (TactiFlex PAF IDE Trial)
Objectives	
The primary objective of the TactiFlex PAF IDE clinical trial is to demonstrate that ablation with the TactiFlex Sensor-Enabled™ Ablation Catheter (TactiFlex SE), in conjunction with a compatible RF generator and three-dimensional mapping system, is safe and effective for the treatment of drug refractory, symptomatic paroxysmal atrial fibrillation (PAF) when following standard electrophysiology mapping and radiofrequency (RF) ablation procedures.
 
The TactiFlex PAF IDE clinical trial has two secondary objectives:
 
 
1. To provide supporting data for the safety and effectiveness of using TactiFlex SE at 40-50 Watts in the left atrium as part of an AF ablation procedure.
 
2. To provide supporting data for the safety and effectiveness of using TactiFlex SE to treat cavo-tricuspid isthmus (CTI)-dependent (or “typical”) atrial flutter (AFL) through the ablation of the CTI in the right atrium. This data may be used to support an expanded indication for the treatment of CTI-dependent AFL.
 

Devices Under Investigation	
Worldwide:
 
 
• TactiFlex Ablation Catheter, Sensor Enabled
 
• EnSite IDE Display Workstation (including Investigational Software Precision v2.5)
 
• TactiSys™ Quartz, TactiFlex™ Ablation Catheter SE RF Cable
 
 
United States Only:
 
 
• Ampere™ Generator (commercial device that is investigational when used in this study)
 
• TactiSys™ Quartz Equipment (commercial device that is investigational when used in this study)
 

Number of Subjects Required	Three hundred fifty-five (355) subjects will be enrolled in this clinical investigation. Three hundred five (305) subjects will be enrolled in the main study and 50 subjects will be enrolled in the HSP substudy.
Clinical Investigation Design	Prospective, non-randomized multi-center clinical investigation. Design includes a main study and a separate substudy. Subjects in the main study are to be treated using the full range of ablation power settings in the IFU. Subjects in the substudy are to be treated in the upper end of the recommended ablation power settings (40-50 Watts).
Primary Safety Endpoint	
The primary safety endpoint is the rate of device and/or procedure-related serious adverse events with onset within 7-days of any ablation procedure that uses the TactiFlex SE catheter (initial or repeat procedure performed between 31-80 days of initial procedure) that are defined below:
 
 
• Atrio-esophageal fistula
 

## Clinical Investigation Plan

	
 
• Cardiac tamponade/perforation
 
• Death
 
• Heart block
 
• Myocardial infarction
 
• Pericarditis
 
• Phrenic nerve injury resulting in diaphragmatic paralysis
 
• Pulmonary edema
 
• Pulmonary vein stenosis
 
• Stroke/cerebrovascular accident
 
• Thromboembolism
 
• Transient ischemic attack
 
• Vagal nerve injury/gastroparesis
 
• Vascular access complications (including major bleeding events)
 
 <hr/> 
1. Atrio-esophageal fistula, cardiac tamponade/perforation and pulmonary vein stenosis will be evaluated through 12-months.
 
2. Bleeding is a major complication of AF ablation if it requires and/or is treated with transfusion or results in a 20% or greater fall in hematocrit.


Primary Effectiveness Endpoint
	
The primary effectiveness endpoint for this clinical trial is freedom from documented (symptomatic or asymptomatic) AF/AFL/AT episodes of >30 seconds duration that are documented by 12-lead ECG, transtelephonic monitoring (TTM) or Holter monitor after the initial catheter ablation procedure through 12-months of follow-up (9 months after a 90-day blanking period).
 
AF/AFL/AT recurrence during the 90-day blanking period (≤90 days post-initial procedure) will not be considered a treatment failure. One repeat procedure will be allowed for ablation of AF/AFL/AT recurrence 31-80 days after the initial procedure and will not be considered a treatment failure. Failure to achieve acute procedural success (confirmation of entrance block after a 20-minute minimum waiting period) during the last ablation procedure with the TactiFlex SE catheter will constitute failure to achieve this endpoint. After the 90-day blanking period, use of Class I or III AADs will not count as a therapy failure provided that only previously failed Class I or Class III AADs are taken at doses that do not exceed the previously failed dose.
 
AF/AFL/AT recurrence will only be assessed by 12-lead ECG, TTM, and Holter monitoring devices for assessment of this primary endpoint so that all subjects are monitored equally with devices of the same sensitivity and specificity (recurrence data collected from other devices such as pacemakers, ICDs, or ICMs will not be included in the assessment). ECG, TTM, and Holter data collected from sites will be evaluated by a core laboratory to ensure independent and unbiased assessment of AF/AFL/AT recurrence for endpoint analysis.
 <hr/> 
1. For subjects that have a repeat ablation procedure ≤80 days after the initial procedure, only failure to achieve acute procedural success during the repeat procedure will contribute to primary effectiveness endpoint.

## Clinical Investigation Plan

Powered Secondary Endpoints	
AAD-Free Secondary Effectiveness Endpoint
 
The AAD-Free Secondary Effectiveness Endpoint has the same definition as the Primary Effectiveness endpoint, except that any use of Class I or III AADs after the 90-day blanking period will count as a therapy failure in this analysis.
 
Single-Procedure Secondary Effectiveness Endpoint
 
The Single-Procedure Secondary Effectiveness Endpoint has the same definition as the Primary Effectiveness endpoint, except that any repeat ablation in the left atrium will count as a failure.
 
Symptomatic Secondary Effectiveness Endpoint
 
The Symptomatic Secondary Effectiveness Endpoint has the same definition as the Primary Effectiveness endpoint, except that documented recurrence without documented evidence of symptoms after the 90-day blanking period will not count as a therapy failure in this analysis.

HSP Substudy Endpoints	
The endpoints for the HSP substudy will be defined the same as the Primary and Secondary Endpoints for the main study. Results will be reported descriptively using summary statistics. No pre-specified hypothesis testing will be performed.
 
The following as-treated analyses will be performed using the Primary and Secondary Endpoint results from main study and HSP substudy subjects.
 
 
1. Results will be summarized separately for subjects that have time-averaged power settings of <math>\geq 40</math> Watts vs. <math>< 40</math> Watts in the left atrium.
 
2. Results will be summarized separately for subjects that have <math>\geq 50\%</math> vs. <math>< 50\%</math> of lesions in the left atrium with power settings <math>\geq 40</math> Watts.
 
3. Results will be summarized separately for subjects that have <math>\geq 25\%</math> vs. <math>< 25\%</math> of lesions in the left atrium with power settings <math>\geq 40</math> Watts.
 

Subject Follow-up	
Baseline, Procedure, Pre-Discharge, 7-day, 5-week, 3-month, 6-month, 12-month
 
 
• The 7-day, 5-week, and 6-month visits are phone calls to the subject
 
• Baseline, Procedure, Pre-Discharge, 3-month, and 12-month visits are in-person
 

Inclusion Criteria	
 
1. Plans to undergo a catheter ablation procedure due to symptomatic PAF that is refractory or intolerant to at least one Class I or III antiarrhythmic drug.
 
2. Physician's note indicating recurrent self-terminating AF
 
3. One electrocardiographically documented AF episode within 12-months prior to informed consent/enrollment. Documented evidence of the AF episode must either be continuous AF on a 12-lead ECG or include at least 30 seconds of AF from another ECG device.
 
4. At least 18 years of age
 
5. Able and willing to comply with all trial requirements
 
6. Informed of the nature of the trial, agreed to its provisions and has provided written informed consent as approved by the Institutional Review Board/Ethics Committee (IRB/EC) of the respective clinical trial site.
 

Exclusion Criteria	
 
1. Persistent or long-standing persistent atrial fibrillation
 
2. Active systemic infection
 
3. Known presence of cardiac thrombus
 
4. Hypertrophic cardiomyopathy
 
5. Arrhythmia due to reversible causes including thyroid disorders, acute alcohol intoxication, and other major surgical procedures in the 90-day period preceding procedure
 

